9.4. LABORATORY EVALUATIONS

All blood and urine samples will be analyzed using a local laboratory. The sampling will be performed at the site at Screening (Visit 1), Visit 4 (Week 13), and Visit 5 (Week 26) and as soon as possible following the premature discontinuation visit (if applicable).

The following parameters will be measured:

- Hematology: hemoglobin, hematocrit, red blood cells, mean corpuscular hemoglobin (MCH), mean corpuscular volume (MCV), mean corpuscular hemoglobin concentration, large unstained cells, white blood cells, lymphocytes, monocytes, neutrophils, eosinophils, basophils and platelets.
- Chemistry: creatinine, uric acid, urea, aspartate aminotransferase (ASAT), alanine aminotransferase (ALAT), albumin, gamma-glutamyltransferase (GGT),

total protein, sodium, potassium, chloride, calcium, phosphorus, glucose, alkaline phosphatase, total bilirubin, total testosterone, free testosterone, Sex Hormone Binding Globulin (SHBG) and prolactin.

- Urinalysis: bilirubin, blood, clarity, color, glucose, ketones, leukocyte esterase, nitrite, pH, protein, specific gravity and urobilinogen.

All summaries of hematology, chemistry and urinalysis will be based on results in standard international (SI) system of units, conversion will be performed according to the data management plan (DMP) prior to the transfer to INC Research. The high and low classifications will be derived relative to the result and normal range in SI units.

Summary tables for hematology, chemistry and urinalysis laboratory variables will include the following: descriptive statistics for SI values and change from baseline for all continuous variables by assessment for each module and dose level. In general, any quantitative assessments for urinalysis will be summarized using the number and percentage of subjects with the given result. Percentages will be calculated out of the number of subjects with non-missing data. Shift tables showing the number of patients having values below, within and above the normal range at each assessment at Screening and each post baseline visit will be presented.

All laboratory results in original and SI units will be included in data listings. Tests will be listed in alphabetical order. Urine drug screen will be listed.

Optional blood sampling for ApoE4 genotyping (e4/e4, e4/e3, e4/e2, e3/e3, e3/e2, e2/e2) will be listed. This data will be collected and reported after DBL.

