3.5. SUBJECT SELECTION

Male and female patients between the ages of 60 and 85 (inclusive) with mild AD.

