4.4. SAFETY ENDPOINTS

The following variables will be collected for assessment of safety:

- Adverse events (including Serious Adverse Events [SAEs]);
- Physical examination;
- Vital signs;
- Concomitant medications;
- Laboratory parameters (hematology, biochemistry [including sex hormones], and urinalysis);
- Electrocardiograms (ECG);
- Sheehan Suicidality Tracking Scale (Sheehan-STS).

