6. GENERAL ASPECTS FOR STATISTICAL ANALYSIS

6.1. GENERAL METHODS

This section describes analytical analysis issues that relate to all or some of the analytic analysis sections that follow. It describes general guidelines for analysis as well as the following items:

- SAS version 9.4 or higher will be used.
- INC Research will be responsible for reporting the demographic, safety, and efficacy data including listings of the administration information for collection of samples.
- Unless otherwise specified, summaries will be presented for each treatment group and dose level and overall.
- The total number of patients in the treatment group and dose level will be used as the denominator for percentage calculations, unless stated otherwise in the table shell.
- Continuous variables will be summarized using the number of observations (n), mean, standard deviation (SD), median, 25th and 75th percentile, 5th percentile and 95th percentile, minimum, and maximum. Categorical variables will be summarized using number of observations (n), frequency and percentages of patients.
- All safety data will be entered in to the patient data listings. All patients entered into the database, including screen failures, will be included in the disposition listings. Patients who are screened only (who have given signed written informed consent) will be presented as a separate group at the end of the appropriate listings.
- All patients who provide informed consent will be accounted for in this study.
- In general, the listings will be sorted by dose level (treatment group), patient number, and assessment date (and time) if applicable.
- The summary tables will include the total column and columns as follows:
 - Placebo, 5 mg piromelatine, 20 mg piromelatine, 50 mg piromelatine.
- Multiple assessments at a given time point (planned, repeat, and unscheduled) will not be included in summary tables unless specified otherwise, but will be included in the listings. For example if there are multiple laboratory results at a given visit/time point, the latest non-missing value within the visit/time point window will be used. See the specific sections of the SAP for further descriptions.
- See [Section 12](#) for INC standard programming conventions.

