9. SAFETY

The safety analysis set will be used for the listing of safety data and for all safety analyses. Safety will be assessed on the basis of adverse event (AE) reports, clinical laboratory data (including sex hormones), ECG parameters, physical examinations, vital signs and suicidal ideation (Sheehan-STS).

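### Sex hormones are summarised with men and women pooled, so by-visit values are hard to interpret and a change confined to one sex is diluted

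*SAP*

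**What the plan says.** Two places in the SAP single out sex hormones. Section 4.4 lists among the safety variables "Laboratory parameters (hematology, biochemistry [including sex hormones], and urinalysis", and the opening of section 9 bases the safety assessment in part on "clinical laboratory data (including sex hormones". Section 3.5 describes the population as "Male and female patients between the ages of 60 and 85 (inclusive) with mild AD".

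Section 9.4 places "total testosterone, free testosterone, Sex Hormone Binding Globulin (SHBG) and prolactin" in the chemistry panel. Its summary rule for all laboratory modules is "descriptive statistics for SI values and change from baseline for all continuous variables by assessment for each module and dose level". It adds "Shift tables showing the number of patients having values below, within and above the normal range at each assessment", with the rule that "The high and low classifications will be derived relative to the result and normal range in SI units". It does not say whether those ranges differ by sex; samples go to local laboratories.

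The default in section 6.1 is "Unless otherwise specified, summaries will be presented for each treatment group and dose level and overall". Section 6.6 defines subgroups by combined dose, ApoE4 status, insomnia and AD medication, for efficacy endpoints only. The index in section 14 has a by-visit table and a shift table for chemistry (14.3.4.1.2.1 and 14.3.4.1.2.2), with no hormone table and no table by sex. The index in section 15 does separate the hormones, in Listing 16.2.8.1.3.

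**The concern.** Sex is the main determinant of level for testosterone, and the plan offers no summary of the hormones that separates men from women. Three consequences follow.

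- By-visit means and SDs mix two distributions. The pooled mean falls between them, and the pooled SD mostly reflects the distance between the sexes.
- Arms with different proportions of men will show different raw means with no drug effect at all.
- A mean change that occurs in one sex only is averaged with the other sex and looks smaller than it is.

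The SAP adjusts its efficacy models for gender, yet does not separate the sexes for the one group of safety analytes in which sex matters most. At stake is how readily a hormonal effect can be recognised and sized from the safety tables. No test or decision rule depends on these tables.

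**Working it through.** The SAP states no hormone mean, SD, effect or test, so there is no figure of its own to reproduce. The check has a reading part and an illustration.

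**Reading.** Sections 6.1, 6.6, 9.4 and 14 agree: laboratory summaries are by assessment and treatment group, and none is by sex. That the hormones fall in the chemistry tables is inferred from section 9.4 together with the table index, since the table shells are separate attachments that are not shown.

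**Inputs to the illustration.**
- From SAP section 3.6: 115 placebo and 95 per dose arm.
- Assumed: share of men p = 0.3 to 0.6. The SD of change in men is set to 1, and that in women is r = 0.05, 0.2 or 1. The effect in men is d = 0.5 SD; the effect in women is e·d, with e = 0, 1 or −1. The gap between the sexes in raw level is G = 2 to 4 male SDs.

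**Raw by-visit values.** Pooled SD = √[p + (1−p)r² + p(1−p)G²], with r here the women-to-men SD ratio of raw values, taken as 0.1 or 1. With p = 0.5, r = 0.1 and G = 3:

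√(0.5 + 0.005 + 2.25) = √2.755 = 1.66 male SDs.

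The pooled mean then lies 1.5 male SDs from each sex's own mean. Over p = 0.3 to 0.6 and G = 2 to 4, the pooled SD is about 1.1 to 2.2 male SDs. A 10-point difference between arms in the share of men moves the raw arm mean by 0.10 × G = 0.2 to 0.4 male SD with no drug effect.

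**Mean change from baseline.** Pooled difference from placebo = p·d + (1−p)·e·d.

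- Men only (e = 0): p·d, so the fraction kept equals p. At 40%, 50% and 60% men, a 0.5 SD change shows as 0.20, 0.25 and 0.30.
- Same in both sexes (e = 1): 0.5, with no dilution.
- Opposite (e = −1): (2p−1)·d. This is −0.10 at 40% men, 0 at 50% and 0.10 at 60%.

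**Signal relative to noise, men-only effect.** The variance is p + (1−p)r² on placebo, plus p(1−p)d² on active. With p = 0.5, r = 0.2 and d = 0.5:

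- Pooled: 0.25 / √(0.52/115 + 0.5825/95) = 0.25 / 0.1032 = 2.42.
- Men alone: 0.5 / √(1/57.5 + 1/47.5) = 0.5 / 0.1961 = 2.55.
- Ratio: 0.95.

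Ratio of pooled z to men-only z:

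| Share of men | Men-only effect, r = 0.05 | Men-only effect, r = 0.2 | Men-only effect, r = 1 | Same effect in both sexes, r = 0.2 |
|---|---|---|---|---|
| 0.3 | 0.95 | 0.92 | 0.54 | 3.19 |
| 0.4 | 0.96 | 0.94 | 0.62 | 2.43 |
| 0.5 | 0.97 | 0.95 | 0.70 | 1.96 |
| 0.6 | 0.97 | 0.96 | 0.76 | 1.64 |

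If women's values hardly vary, pooling costs 3–8% of the z statistic. If both sexes vary equally, it costs 24–46%. If the effect is common to both sexes, pooling gains.

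**The case against.** A reader might infer that the sex-hormone assessment cannot show a drug effect at all. The documents do not support that.

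- Section 9.4 plans change from baseline, which removes each patient's own level and with it the gap between the sexes.
- Section 6.1 requires the median, the 5th, 25th, 75th and 95th percentiles, and the extremes, so a fall confined to men could show in the lower tail of the change.
- Shift tables and a dedicated hormone listing are planned.
- As the table shows, the loss of signal is small when women's values vary little, and an effect common to both sexes is shown better by pooling.

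Two further readings are tempting and wrong. One is to divide a diluted change by the pooled SD of raw levels: the gap between the sexes inflates that SD but is absent from change scores. The other is to set the shift in raw means caused by sex imbalance against the size of a diluted change. Imbalance moves levels; it moves mean change only if the sexes change differently.

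It can also be said that the tables are descriptive, that a by-sex table could be added later, and that the case is clearest for testosterone, with nothing in the SAP to size it for SHBG or prolactin. All of this stands and limits the weight of the point.

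It does not remove it. In a descriptive table the reader judges the mean change itself, and that is diluted whatever the z ratio. Shift tables register only values that cross a limit, and the SAP does not say that the limits are sex-specific. A listing is not a summary. A by-sex table added after the pooled results are seen would be post hoc.

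**Conclusion.** The point holds as a weakness of presentation in a named safety assessment. Pooled by-visit values of strongly sex-dependent hormones describe neither sex and depend on each arm's sex mix. A mean change in one sex is reduced to that sex's share, so to 40–60% of its size in men if 40–60% of patients are men, and opposite changes may cancel. A drug effect can still be seen through the other planned displays, so this is a matter of dilution and interpretability, not of inability to detect.

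The absence of a by-sex summary is read directly from the SAP text and table index, subject to the table shells not being shown. The sizes rest on assumed shares of men, assumed SD ratios and an assumed gap between the sexes, none of which the SAP gives. The dilution of the mean depends on the share of men alone; the z ratios also need the SD and effect assumptions. The primary analysis is unaffected.

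**What to change.** In section 9.4, state that total testosterone, free testosterone, SHBG and prolactin will be summarised separately for men and women within treatment group: by-visit values, change from baseline and shift tables. State also that high and low for these four analytes will be classified against sex-specific normal ranges. In section 14, add a hormone by-visit table and a hormone shift table, both by sex, to match Listing 16.2.8.1.3, and take the four analytes out of the pooled chemistry tables.

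The cost is SAP wording, one extra table pair and fewer patients per cell. Sex and hormone values are already collected. Confirming that each local laboratory supplies sex-specific ranges is a small data-management check.

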1. GLOSSARY OF ABBREVIATIONS

Abbreviation	Description
AD	Alzheimer's Disease
ADAS-cog14	Alzheimer's Disease Assessment Scale cognitive subscale
ADCS-MCI-ADL	Alzheimer's Disease Cooperative Study/Activities of Daily Living scale adapted for MCI patients
AE	Adverse Event
ALAT	Alanine Aminotransferase
ANCOVA	Analysis of Covariance
ASAT	Aspartate Aminotransferase
ATC	Anatomical Therapeutic Chemical
BDRM	Blinded Data Review Meeting
BMI	Body Mass Index
CDR	Clinical Dementia Rating
CFT	Category Fluency Test
CGIC	Clinical Global Impression of Change
CI	Confidence Interval
cNTB	computerized Neuropsychological Test Battery
COWAT	Controlled Oral Word Association Test
CRF	Case Report Form
CTCAE	Common Terminology Criteria for Adverse Events
CV	Coefficient of Variation
DBL	Data Base Lock
DET	Detection
DMC	Data Monitoring Committee
DMP	Data Management Plan
ECG	Electrocardiogram
FAS	Full Analysis Set
FDA	Food and Drug Administration
GCP	Good Clinical Practice

Abbreviation	Description
GGT	Gamma-Glutamyltransferase
ICH	International Council on Harmonization
IDN	Identification
ISLT	International Shopping List Test
IVRS	Interactive Voice Randomization System
IWRS	Interactive Web Randomization System
LOTE	Lack of Therapeutic Efficacy
Max	Maximum
MCH	Mean Corpuscular Hemoglobin
MCI	Mild Cognitive Impairment
MCMC	Markov Chain Monte Carlo
MCV	Mean Corpuscular Volume
MedDRA	Medical Dictionary for Regulatory Activities
Min	Minimum
MMRM	Mixed-effects Maximum likelihood Repeated Measures
MMSE	Mini Mental State Examination
N/A	Not Applicable
NA	Not Applicable
NCI	National Cancer Institute
NPI	Neuropsychiatric Inventory
OBK	One Back Card
OCL	One Card Learning
PPS	Per Protocol Set
PSQI	Pittsburgh Sleep Quality Index
PT	Preferred Term
QC	Quality Control
QTc	Corrected QT Interval
SAE	Serious Adverse Event
SAP	Statistical Analysis Plan

Abbreviation	Description
SD	Standard Deviation
SHBG	Sex Hormone Binding Globulin
Sheehan-STS	Sheehan Suicidality Tracking Scale
SE	Standard Error
SI	Standard International System of Units
SOC	System Organ Class
SOP	Standard Operating Procedure
SS	Safety Analysis Set
STS	Suicidality Tracking Scale
TEAE	Treatment Emergent Adverse Event
TLF	Table, Listing and Figure
VAS	Visual Analogue Scale
WHO	World Health Organization

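### No planned laboratory table counts patients with large liver-test rises by arm, keeps a peak that is followed by a lower repeat, or pairs aminotransferase with bilirubin in the same patient

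*SAP*

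**What the plan says.** SAP Section 9.4 measures ASAT, ALAT, alkaline phosphatase, GGT and total bilirubin at Screening, Week 13 and Week 26, and after premature discontinuation. On the source of the results it states: "All blood and urine samples will be analyzed using a local laboratory".

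It plans two kinds of summary:

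- By-visit statistics: "descriptive statistics for SI values and change from baseline for all continuous variables by assessment for each module and dose level". Section 6.1 fixes the statistics for continuous variables. Besides n, mean, SD, median and quartiles they include the "5th percentile and 95th percentile, minimum, and maximum".
- Shift tables: "Shift tables showing the number of patients having values below, within and above the normal range at each assessment". The cut is set by this rule: "The high and low classifications will be derived relative to the result and normal range in SI units".

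The index in Section 14 matches. Chemistry has Table 14.3.4.1.2.1 (results by visit) and Table 14.3.4.1.2.2 (shift from baseline), and nothing else.

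Section 6.1 also decides which result enters a summary. Repeat and unscheduled assessments stay out of the tables unless a section says otherwise. Where a visit window holds several laboratory results, the last non-missing one is used. Section 9.4 makes no exception. All results go into the listings (chemistry is Listing 16.2.8.1.2).

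**The concern.** A liver signal that matters for a dose decision is usually a handful of patients with large rises, perhaps with bilirubin rising too. Three questions follow for each arm: how many patients had a large rise, how high did each go at worst, and did bilirubin rise in the same patient?

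The planned tables answer none of these directly. The shift table has one category for everything over the upper limit. The by-visit table gives distribution statistics for one parameter at a time. Both take the last result in a window, so a high value that prompted a repeat can be replaced by that repeat.

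Section 3.4 describes the trial as a dose-ranging study of safety as well as efficacy. A by-arm count of marked abnormalities is therefore part of what its tables should deliver.

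**Working it through.** The SAP states no figure on this point, so there is none to reproduce. The check sets the sections side by side and adds a small calculation of what the planned tables would show.

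**1. Size of a rise in the shift table.** Section 9.4 classifies a result against the normal range only. Assume an upper limit of 40 U/L for ALAT (not in the SAP). A value of 41 U/L is 41/40 = 1.03 times the limit, and 400 U/L is 400/40 = 10 times. Both fall in the above-range category. The shift format separates patients who were already high at Screening from new cases, but it does not grade the new cases.

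**2. What the by-visit table would show.** Inputs: 460 randomised at 1.2:1:1:1 (Section 3.6) gives 460/4.2 = about 110 per piromelatine arm. Assumed, not in the SAP: SD of change 10 U/L without a signal, and two patients with an added rise of r.

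SD of change = √(10² + p(1 − p)r²), with p = 2/110 and p(1 − p) = 0.01785.

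- r = 180: √(100 + 578.4) = 26.0; maximum change at least 180.
- r = 100: √(100 + 178.5) = 16.7; maximum change at least 100.
- With the assumed SD halved to 5 or doubled to 20: 24.6 and 31.3 for r = 180; 14.3 and 24.1 for r = 100.

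So if the values enter the table, the SD and the maximum show that something happened in that arm. They do not say to how many patients. The maximum is the same for one patient as for two. The 95th percentile does not help either: 5% of 110 is 5.5, so up to five patients with large rises lie above it.

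**3. Whether the values enter the table.** Take a patient whose ALAT in the Week 13 window is 8 times the upper limit and whose repeat in the same window is back in range. Section 6.1 selects the repeat. Both planned tables then show an in-range Week 13 value. A peak at an unscheduled visit outside any window has no row in a by-visit table. With scheduled post-baseline sampling only at Weeks 13 and 26, off-schedule results may hold much of the information on peaks. Section 9.4 also does not say which row of the tables takes the premature-discontinuation sample.

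**4. Enzyme and bilirubin together.** ALAT, ASAT and total bilirubin are each summarised as separate parameters. No indexed table crosses them within patient.

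**5. Are the data in hand?** Yes. The high and low flags already need each result together with its normal range, so the ratio to the upper limit can be derived from the same records.

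**The case against.** The best case on the other side is that Section 9.4 is consistent with the index and misstates nothing, so the request is only for an extra table. It has several parts.

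- **The extremes are visible.** Change from baseline, SD, 95th percentile and maximum are all planned, and step 2 above shows that two large rises would alter the SD and maximum plainly. This stands for values that reach the table. A reader might infer that a large rise would be invisible, or that the trial would report no laboratory signal when one is present. The documents do not support that.
- **Everything is listed.** Section 12.2.5.3 sorts listings by treatment, subject and visit, so one patient's ALAT and bilirubin can be read together. This stands too. It would be wrong to say that the two are never linked; the gap is in the summaries. A hand search of listings is still not a prespecified count by arm.
- **No laboratory test is planned.** Review is descriptive, so arguments from P values or from dilution of an arm mean are beside the point. Agreed; none is used here.
- **The adverse event tables may catch the cases.** They may, if the protocol (not shown) requires abnormal results to be reported as events. Those tables count terms and severity, not multiples of the upper limit.
- **The table shells are not shown.** True, but the index lists every table by number, and none is of this kind.

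A reader might also take the glossary entry "Common Terminology Criteria for Adverse Events" as a sign that laboratory grading was intended and lost. The entry fits adverse event grading, since Section 9.3 assigns Grade 3 to events with missing severity. It is no evidence about laboratory data.

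**Conclusion.** The point holds as a gap in the planned summaries. No table counts patients with a large rise by arm. The Section 6.1 rule can remove a peak from both chemistry tables. No summary shows joint enzyme and bilirubin rises.

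Its size cannot be given as a number: the SAP reports no liver findings, no expected rate of abnormal values and no count of unscheduled samples. It does not affect any efficacy conclusion, and it does not hide data, because all results are listed and extremes that enter the tables show in the maximum and SD. The figures above rest on assumed values and serve only to show what the planned statistics would and would not reveal.

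Scaling to the upper limit matters further if sites use laboratories with different ranges. The wording on local analysis suggests this but does not state it. The change is worth making because it is cheap and replaces a last-value, three-category display with a worst-value count.

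**What to change.** Add one table to Section 9.4 and the index, on the Safety Analysis Set:

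- number and percentage of patients per arm by worst post-baseline value of ALAT, ASAT, alkaline phosphatase and total bilirubin, in multiples of the reporting laboratory's own upper limit;
- scheduled, repeat, unscheduled and discontinuation samples all included;
- the number of patients per arm with both an aminotransferase and a bilirubin rise.

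The sponsor sets the multiples, and the rule for counting a joint rise, before unblinding. Section 9.4 should state that this table is an exception to the Section 6.1 rule on repeat, unscheduled and latest values. The by-visit and shift tables can stay as they are.

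Cost: a few sentences in the SAP and one program using results and ranges already collected. The downside is one more table with small counts, to be read descriptively.
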